### 1.3 Research Design and Methods

#### A. Research Procedures

In this study we will treat patients with AML, MDS and advanced myeloproliferative disorders with decitabine, venetoclax and salsalate. 5-azacytidine may be substituted for decitabine if the patient has been previously treated with decitabine. Patients will be hospitalized for initiation of therapy (for at least 4 days). Venetoclax dose escalation in cycle 1 will follow the recommended “ramp up” to minimize the risk of tumor lysis. Salsalate will be added on day 5 of decitabine + venetoclax (or 5-azacytidine). There will be only one cycles of treatment with salsalate. The next treatment cycle will be administered under the direction of the treating physician.

Cycle 1:

- i. Venetoclax and decitabine (or 5-azacytidine) will initiate concurrently on d1; salsalate will be start on d5.
  1. Decitabine 20 mg/m^2/d IV will be administered d1-10. If 5-azacytidine is being used (if the patient has previously been exposed to decitabine) it will be administered at 75 mg/m^2/d SC or IV d1-7.
  2. Venetoclax will be dose escalated per package insert - 100 mg d1; 200 mg d2; and 400 mg d3-28.
  3. Salsalate 1500 mg PO bid will start on day 5 of decitabine (or 5-azacytidine) and be administered until and including the day of completion of the decitabine or 5-azacytidine.

Patients with WBC greater than 25,000/uL will be treated with hydroxyurea 2-3g PO bid per treating physician to obtain a WBC<15,000/uL. Once WBC is in target range the protocol treatment can be started. Hydroxyurea may be continued to sustain WBC < 15,000/uL as needed. Standard tumor lysis monitoring and prophylaxis will be used. Allopurinol (or alternate hypouricemic agent) will be started  $\geq$ 24 h prior to starting venetoclax and continued through dose escalation of venetoclax, or longer, as clinically indicated. During dose escalation of venetoclax patients will receive IV fluids, and tumor lysis laboratory studies (basic chemistry profile including calcium, phosphate, uric acid and lactate dehydrogenase) will be obtained every 8 hours.

Infectious disease prophylaxis may be used at the discretion of the patients treating physician. If anti-fungal prophylaxis is used the dose of venetoclax will be modified as outlined below. Proton pump inhibitors are mandated unless there is a contraindication. Venetoclax dosing will be adjusted if concurrent anti-infectives are CYP3A4 or Pgp inhibitors (see below).

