Patients that are not hospitalized will be asked to keep a medication diary and instructed to record the number of capsules taken and the time taken. At the end of each cycle of treatment, the actual amount of unused drug will be compared to the amount taken as recorded on the subject's medication diary.

All patients who receive one dose of protocol therapy will be evaluable for assessment of toxicity. Prior to each cycle the treating physician will fully assess the patient's condition with respect to possible treatment related toxicities. All adverse events, whether observed by the physician or reported by the patient, occurring during the active portion of therapy, or up to 30 days after the last dose of treatment will be graded by a numerical score according to the NCI's Common Terminology Criteria for Adverse Events (CTCAE), Version 5.0 (<http://ctep.cancer.gov/reporting/ctc.html>) and recorded in the patient's medical record. For the purposes of reporting laboratory abnormalities, only Grade 3-4 adverse events will be recorded on the adverse event CRF pages. Grade 1-2 laboratory abnormalities will not be recorded on the adverse event CRF pages. Information entered on the adverse event CRF pages will include:

- Specific type and duration of reaction (i.e., start and stop dates, resolution).
- Severity/grade.
- Relationship to study drug (causality, attribution).
- Management of the event, if treated with medication and other actions taken to alleviate the clinical event.
- Whether or not it was considered a SAE.

A preexisting condition is one that is present at the start of the study. A preexisting condition will be recorded as an adverse event if the frequency, intensity, or the character of the condition worsens during the study period.

An adverse experience is defined as any unintended or abnormal clinical observation that is not of benefit to the patient. Either the condition was not present prior to exposure to the study therapy, or it has worsened in intensity or frequency following exposure to the study therapy.

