#### **4.7 Risks of Harm/Potential for Benefits to Subjects**

##### **A. Description of Risks of Harm to Subjects**

MDS, AML and related advanced myeloid disorders are life-threatening diseases. Risks of the disease include bleeding, infection and organ dysfunction. The disease is fatal with standard chemotherapy in > 80% patients eligible for this study over a 2 years. The combination of venetoclax + hypomethylating agent therapy is a breakthrough – greatly improving response rates and, likely, also survival. The potential risks of this study are that there will be toxicity from the study drug related to known SALSALATE toxicities (e.g tinnitus, renal insufficiency) or that it will interfere with the anti-leukemic effect of venetoclax + hypomethylating agent. To protect against or minimize potential risks, we will monitor toxicity real time and have imposed very strict stopping rules.

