#### **6.0 Data Management Plan**

##### **6.1 Data Analysis**

1. An unacceptable adverse event is defined as a Grade 3 study drug (SALSALATE) related or possibly related irreversible (i.e. doesn't reverse within one week) event with the exception of:
  - a. Grade 3 fever, asthenia or constipation.
  - b. Grade 3 nausea, vomiting, diarrhea (not requiring tube feeding, total parenteral nutrition, or prolonged hospitalization;
  - c. Grade 3 infection, bleeding or expected complications of cytopenias due to leukemia or decitabine + venetoclax treatment;
  - d. Grade 3 or 4 tumor lysis syndrome successfully managed clinically that resolves within 7 days without end organ damage; or
  - e. Grade 3 or 4 isolated electrolyte abnormalities that last < 72 hours.

We consider an adverse event rate of 7% or higher to be unacceptably high, so we will stop the trial if, at any point, we are 80% certain that the rate is 7% or higher. In the following table, the shaded cells in the table indicate the region where we are 80% certain that the rate exceeds 7%.

According to this table, if there is 1 unacceptable (grade 3) SALSALATE related or possibly related adverse event (defined above) among the first 10 patients, or if there are 2 unacceptable adverse events among the first 20 patients, the trial will be stopped for unacceptable toxicity.

This table was calculated using a Bayesian posterior beta distribution, assuming a uniform prior.

N patients      k: number of unacceptable toxicities

	0	1	2	3
3	0.748052	0.973272	0.9987	0.999976
4	0.695688	0.957507	0.99692	0.999887
5	0.64699	0.939179	0.994161	0.999679
6	0.601701	0.918726	0.990312	0.999293
7	0.559582	0.896534	0.985301	0.998664
8	0.520411	0.872948	0.979088	0.997729
9	0.483982	0.84827	0.971658	0.996424
10	0.450104	0.82277	0.963021	0.99469
11	0.418596	0.796683	0.953203	0.992473
12	0.389295	0.770217	0.942247	0.989724
13	0.362044	0.743553	0.930205	0.986401
14	0.336701	0.716847	0.917139	0.982467
15	0.313132	0.690237	0.903119	0.977894
16	0.291213	0.663839	0.888217	0.97266
17	0.270828	0.637756	0.87251	0.966749
18	0.25187	0.612071	0.856078	0.960152
19	0.234239	0.586857	0.838997	0.952867
20	0.217842	0.562173	0.821347	0.944896

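### Does section 6.1 give two stopping rules that contradict each other, one by 80% certainty and one by event count?

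*Combined protocol and SAP*

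**What the plan says.** Section 6.1 (Data Analysis) sets the standard first: "We consider an adverse event rate of 7% or higher to be unacceptably high", and "we will stop the trial if, at any point, we are 80% certain that the rate is 7% or higher". A table of posterior probabilities follows for 3 to 20 patients and 0 to 3 events. From that table the section draws its counts: the trial stops "if there is 1 unacceptable (grade 3) SALSALATE related or possibly related adverse event (defined above) among the first 10 patients", or with two such events in the first 20. The model is given in one line: "This table was calculated using a Bayesian posterior beta distribution, assuming a uniform prior".

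Two other features bear on timing. To count, an event must be an "irreversible (i.e. doesn't reverse within one week) event", so it cannot be classified on the day it starts. Section 1.3 A (Research Procedures) says that adverse events "occurring during the active portion of therapy, or up to 30 days after the last dose of treatment will be graded". The section on risks of harm (4.7 A) tells the reader that "we will monitor toxicity real time and have imposed very strict stopping rules".

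The plan does not define N as patients treated or as patients with a known outcome, and gives no minimum N in words.

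**The concern.** A stopping rule should give one answer for each state of the data, and this is the plan's only numerical decision rule for its primary, tolerability objective. Both sentences in section 6.1 are worded as operative, and nothing says which prevails.

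- **Zero events.** The uniform prior puts most of its weight above 7%, so a literal reading of the 80% sentence stops the trial before anyone is treated, and again after one or two patients without toxicity. The count sentence would not.
- **Late recognition.** Suppose patient 10 has an unacceptable event that is recognised after patient 11 has been counted. The count sentence says stop. The table's cell for 1 event in 11 patients is below 80%, so the probability sentence says continue.

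The one-week persistence test and the 30-day collection window make some delay plausible, and no passage holds accrual until the previous patient's outcome is known. If the wrong sentence were followed, the trial could continue past its own printed boundary.

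**Working it through.** **Inputs.** Threshold 7%, certainty 80%, uniform prior, counts 1 in 10 and 2 in 20 (all section 6.1); 20 patients over 3 years (section 1.5); weekly data review (section 6.3 A).

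**1. Reproduce the table.** The posterior is Beta(1+k, 1+n−k), and P(rate > 0.07) equals P(Bin(n+1, 0.07) ≤ k).

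- 0/3: 0.93^4 = 0.748052.
- 1/10: 0.93^11 + 11 × 0.07 × 0.93^10 = 0.450104 + 0.372666 = 0.822770.
- 1/11: 0.93^12 + 12 × 0.07 × 0.93^11 = 0.418596 + 0.378087 = 0.796683.

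These match the printed cells. All 72 cells reproduce to rounding (largest difference 5 × 10⁻⁷).

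**2. Compare the boundaries.** The smallest number of events giving at least 0.80 is 1 for n = 3 to 10 and 2 for n = 11 to 20, exactly the count rule. The two-event column is still 0.821347 at n = 20, so the two-in-20 part can never conflict. Any conflict is confined to zero events before n = 3, or to a single event among the first 10 patients.

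**3. Zero events.** The posterior is 0.93^(n+1): 0.930 at n = 0, 0.865 at n = 1, 0.804 at n = 2, 0.748 at n = 3. The first figure is simply the prior. The table has no rows for n = 0 to 2, and no printed zero-event cell reaches 0.80.

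**4. Late recognition, N = patients treated (an assumption).** Let an outcome become known L patients late. The statements give opposite answers on the first event when it falls in patients 11−L to 10, with probability Σ p(1−p)^(i−1).

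| True rate | L = 1 | L = 2 |
|---|---|---|
| 3% | 2.3% | 4.6% |
| 7% | 3.6% | 7.6% |
| 15% | 3.5% | 7.6% |

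At 7% with L = 1 this is 0.07 × 0.93^9 = 0.07 × 0.520411 = 0.0364.

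Total stopping probability under the counts is 1−(1−p)^10 + (1−p)^10 × P(Bin(10, p) ≥ 2). At 7% this is 0.516 + 0.073 = 0.589. Under the 80% sentence, with at least one event required, it is 57% (L = 1) or 55% (L = 2). At 3% the figures are 29% against 27% or 25%.

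**5. Late recognition, N = patients with known outcome.** If outcomes settle in patient order, the event in patient i is always assessed at n = i, whatever the delay. L drops out and the statements agree throughout n = 3 to 20. A conflict remains only if a later outcome settles first. For patient 10 overtaken by an event-free patient 11, the probability is at most p(1−p)^10. At 7% this is 0.07 × 0.483982 = 3.4%, and only if overtaking were certain.

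**6. Is a long delay likely?** Even accrual (an assumption) gives 3 × 365 / 20 ≈ 55 days between patients. Salsalate ends on day 7 or day 10 with the hypomethylating agent, and venetoclax is scheduled as "100 mg d1; 200 mg d2; and 400 mg d3-28". Adding 30 days gives day 37, 40 or 58; adding the one-week test gives day 44, 47 or 65. The first two fall before the next average enrolment, and the third before the one after (about day 110). Delays of two or more patients would need clustered accrual.

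**The case for a change.** The best case for a change is that the plan leaves N undefined, that the 80% sentence read alone suggests using whoever has been counted at that moment, and that one clause would remove the doubt at no cost in patients. Weekly review cannot abolish the one-week persistence test. Nor is the follow-up window for this rule settled: section 6.1 does not tie the rule to the 30-day collection period, the Endpoints section speaks of toxicity over two cycles, and a footnote to the schedule in section 1.3 A puts end of treatment 45 days after the last salsalate dose. The day figures above are therefore illustrative. Enrolment may also cluster.

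What stands is that the denominator is undefined and no minimum N is written. It does not follow that the two statements conflict in use. A beta-binomial posterior for k events in n patients is built from observed outcomes; entering a patient with a pending outcome as a non-event misapplies the table. The count sentence also attaches the event to a patient among the first 10, not to the date of recognition, so it already stops the trial for a late-recognised event. A clause saying that the counts govern would repeat this.

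**Conclusion.** No change is needed. Section 6.1 runs as one chain, from the 80% standard to a table starting at three patients to counts read off that table, and the counts are what the trial team would apply. The zero-event result is a property of the uniform prior outside the printed range and would not be acted on.

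The late-recognition conflict is an ambiguity about N that analysts would fill sensibly, by counting patients whose outcome is known. The statements then agree for n = 3 to 20, apart from the case where patient 11 settles before patient 10. Under the less natural treated-patient denominator, a one-patient delay produces disagreement on the first event in 2.3% to 3.6% of trials at true rates of 3%, 7% and 15%, and lowers total stopping probability at 7% from 59% to 57%. Larger effects need a two-patient delay, which even accrual of 20 patients over 3 years makes unlikely. Where the two readings do part over a late event, the explicit count sentence is the stricter one. Following the plan as written gives a sound stopping decision.

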## 6.2 Data Security

Monitoring of this study will occur in accordance with the Cancer Institute of New Jersey's NCI approved Data and Safety Monitoring Plan (DSMP). An "initiation audit" will be conducted at the Cancer Institute of New Jersey in accordance with the DSMP following enrollment of the first two (2) or three (3) patients. Subsequent audits will occur on an annual basis prior to annual IRB continuing review, if the findings from the initiation audit were satisfactory. More frequent audits of patient data and study conduct will occur if necessary. Prior audit findings and/or situations that may arise during the course of the study will determine the need for more frequent auditing. All audit findings will be discussed with the principal investigator and reported to the Cancer Institute of New Jersey's Human Research Oversight Committee and the Rutgers University Institutional Review Board.

## 6.3 Data and Safety Monitoring

### A. Data/Safety Monitoring Plan

A subset of the National Cancer Institute (NCI) CRFs, in electronic format, will be utilized. Completion of the electronic CRFs (eCRFs) will be done in accordance with the instructions in a study specific data capture plan. All eCRFs will be completed by clinical research coordinators of the Office of Human Research Services (OHRS) at the Cancer Institute of New Jersey. The eCRFs will be maintained in a confidential format in a secure database.

Completion of eCRFs will occur in accordance with NCI guidelines. Baseline (pre-study) eCRFs (e.g., enrollment, medical history, concomitant medications, disease assessment, etc.) will be completed no later than 14 days after the start of treatment. Treatment eCRFs (e.g., drug administration, adverse events, chemistries, etc.) will be completed no later than 14 days following each cycle of treatment. Off-treatment information (e.g., follow-up, best response, etc.) will be completed no later than 14 days after the end of protocol treatment.

A research chart (i.e., shadow chart) is maintained at OHRS for each patient enrolled. Copies of significant study source documents will be maintained in the research chart. Examples of source document copies that will be maintained in the research chart include: signed informed consent form, documents that verify eligibility and treatment and documents that verify Grade 3-4 adverse events and response. This information will be updated on a prospective basis and will be confidentially maintained at the Cancer Institute of New Jersey, OHRS.

Data will be analyzed weekly by the PI with review at weekly tumor study group meetings including research nurses assigned to the study.

### B. Data/Safety Monitoring Board Details

## 6.4 Reporting Results

### A. Individual Subjects' Results

Results of investigational diagnostic tests, genetic tests, or incidental findings will not be shared with study participants unless that information is the same as would be shared if the patient was not enrolled in this trial.

**B. Aggregate Results**

Aggregate research results will not be shared with the study participants.

**C. Professional Reporting**

The policies and procedures of Rutgers University's legal department (see: Investigator's Handbook) will govern publication of the trial. It is expected that the results of this trial will be submitted for publication in a timely manner following the conclusion. The Cancer Institute of New Jersey PI, and all co-authors prior to submission or use, must review any abstract or manuscript.

**D. Clinical Trials Registration, Results Reporting and Consent Posting**

This research qualifies as a clinical trial

**6.5 Secondary Use of the Data**

There will be no secondary use of the data.

**7.0 Research Repositories – Specimens and/or Data**

Specimens will not be stored for use other than outlined in the study.

**8.0 Approvals/Authorizations**

N/A

**1.1 Appendix A**  
**Performance Status Criteria**

ECOG Performance Status Scale		Karnofsky Performance Scale	
Grade	Descriptions	Percent	Description
0	Normal activity. Fully active, able to carry on all pre-disease performance without restriction.	100	Normal, no complaints, no evidence of disease.
		90	Able to carry on normal activity; minor signs or symptoms of disease.
1	Symptoms, but ambulatory. Restricted in physically strenuous activity, but ambulatory and able to carry out work of a light or sedentary nature (e.g., light housework, office work).	80	Normal activity with effort; some signs or symptoms of disease.
		70	Cares for self, unable to carry on normal activity or to do active work.

2	In bed <50% of the time. Ambulatory and capable of all self-care, but unable to carry out any work activities. Up and about more than 50% of waking hours.	60	Requires occasional assistance, but is able to care for most of his/her needs.
		50	Requires considerable assistance and frequent medical care.
3	In bed >50% of the time. Capable of only limited self-care, confined to bed or chair more than 50% of waking hours.	40	Disabled, requires special care and assistance.
		30	Severely disabled, hospitalization indicated. Death not imminent.
4	100% bedridden. Completely disabled. Cannot carry on any self-care. Totally confined to bed or chair.	20	Very sick, hospitalization indicated. Death not imminent.
		10	Moribund, fatal processes progressing rapidly.
5	Dead.	0	Dead.
